## 5.3 Eligibility Criteria

### 5.3.1 General Eligibility Criteria

Assessment for general eligibility criteria is based on medical records of the site and interview with a candidate subject. If some of the clinical and laboratory tests are not included in site standard tests, they must be done but after written informed consent is obtained. Subjects must meet ALL of the inclusion criteria to be considered for the clinical evaluation. If ANY of the exclusion criteria are met, the subject is excluded from the clinical evaluation and cannot be registered.

### **5.3.1.1 General Inclusion Criteria**

1. Subject is considered at high risk for bleeding (HBR), defined as meeting one or more of the following criteria at the time of registration and in the opinion of the referring physician, the risk of major bleeding with > 3-month DAPT outweighs the benefit:
  - a)  $\geq 75$  years of age.
  - b) Clinical indication for chronic (at least 6 months) or lifelong anticoagulation therapy.
  - c) History of major bleeding which required medical attention within 12 months of the index procedure.
  - d) History of stroke (ischemic or hemorrhagic).
  - e) Renal insufficiency (creatinine  $\geq 2.0$  mg/dl) or failure (dialysis dependent).
  - f) Systemic conditions associated with an increased bleeding risk (e.g. hematological disorders, including a history of or current thrombocytopenia defined as a platelet count  $<100,000/\text{mm}^3$ , or any known coagulation disorder associated with increased bleeding risk).
  - g) Anemia with hemoglobin  $< 11\text{g/dl}$ .
2. Subject must be at least 18 years of age.
3. Subject or a legally authorized representative must provide written informed consent as approved by the Institutional Review Board (IRB)/Ethics Committee (EC) of the respective clinical site prior to any study related procedure.
4. Subject is willing to comply with all protocol requirements, including agreement to stop taking P2Y12 inhibitor at 3 months, if eligible per protocol.
5. Subject must agree not to participate in any other clinical trial for a period of one year following the index procedure.

### **5.3.1.2 General Exclusion Criteria**

1. Subject with an indication for the index procedure of acute ST-segment elevation MI (STEMI).
2. Subject has a known hypersensitivity or contraindication to aspirin, heparin/bivalirudin, P2Y12 inhibitors (clopidogrel/prasugrel/ticagrelor), everolimus, cobalt, chromium, nickel, tungsten, acrylic and fluoro polymers or contrast sensitivity that cannot be adequately pre-medicated.
3. Subject with implantation of another drug-eluting stent (other than XIENCE) within 9 months prior to index procedure.
4. Subject has a known left ventricular ejection fraction (LVEF)  $<30\%$ .
5. Subject judged by physician as inappropriate for discontinuation from P2Y12 inhibitor use at 3 months, due to another condition requiring chronic P2Y12 inhibitor use.

6. Subject with planned surgery or procedure necessitating discontinuation of P2Y12 inhibitor within 3 months following index procedure.
7. Subject with a current medical condition with a life expectancy of less than 12 months
8. Subject intends to participate in an investigational drug or device trial within 12 months following the index procedure.
9. Pregnant or nursing subjects and those who plan pregnancy in the period up to 1 year following index procedure. Female subjects of child-bearing potential must have a negative pregnancy test done within 7 days prior to the index procedure per site standard test.

**Note:** Female patients of childbearing potential should be instructed to use safe contraception (e.g., intrauterine devices, hormonal contraceptives: contraceptive pills, implants, transdermal patches, hormonal vaginal devices, injections with prolonged release.) It is accepted, in certain cases, to include subjects having a sterilised regular partner or subjects using a double barrier contraceptive method. However, this should be explicitly justified in special circumstances arising from the study design, product characteristics and/or study population.

10. Subject is part of a vulnerable population, defined as subject whose willingness to volunteer in a clinical investigation could be unduly influenced by the expectation, whether justified or not, of benefits associated with participation or of retaliatory response from senior members of a hierarchy in case of refusal to participate. Examples of populations which may contain vulnerable subjects include: individuals with lack of or loss of autonomy due to immaturity or through mental disability, persons in nursing homes, children, impoverished persons, subjects in emergency situations, ethnic minority groups, homeless persons, nomads, refugees, and those incapable of giving informed consent. Other vulnerable subjects include, for example, members of a group with a hierarchical structure such as university students, subordinate hospital and laboratory personnel, employees of the sponsor, members of the armed forces, and persons kept in detention.
11. Subject is currently participating in another clinical trial that has not yet completed its primary endpoint.

### **5.3.2 Angiographic Eligibility Criteria**

All angiographic eligibility criteria are based on visual assessment.

#### **5.3.2.1 Angiographic Inclusion Criteria**

1. Up to three target lesions with a maximum of two target lesions per epicardial vessel.

Note:

- The definition of epicardial vessels means left anterior descending coronary artery (LAD), left circumflex coronary artery (LCX) and right coronary artery (RCA) and their branches. For example, the patient must not have >2 lesions requiring treatment within both the LAD and a diagonal branch in total.

- If there are two target lesions within the same epicardial vessel, the two target lesions must be at least 15 mm apart per visual estimation; otherwise this is considered as a single target lesion.

2. Target lesion  $\leq$  32 mm in length by visual estimation.
3. Target lesion must be located in a native coronary artery with visually estimated reference vessel diameter between 2.25 mm and 4.25 mm.
4. Exclusive use of XIENCE family of stent systems during the index procedure.
5. Target lesion has been treated successfully, which is defined as achievement of a final in-stent residual diameter stenosis of  $<20\%$  with final TIMI-3 flow assessed by online quantitative angiography or visual estimation, with no residual dissection NHLBI grade  $\geq$  type B, and no transient or sustained angiographic complications (e.g., distal embolization, side branch closure), no chest pain lasting  $> 5$  minutes, and no ST segment elevation  $> 0.5$  mm or depression lasting  $> 5$  minutes.

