### **5.4 Subject Registration**

Subject registration will occur after the index procedure but prior to discharge and up to 3 days post index procedure, upon confirmation of the following:

- Signed informed consent has been obtained;
- Subject has met all the inclusion and none of the exclusion criteria (including both general and angiographic criteria).

Planned staged procedures are allowed (recommend to be performed within 30 days). The site may consent the subject after the initial procedure. Subject registration will occur once the last staged procedure is performed, and the last staged procedure is considered as the index procedure.

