## 6.2 Index Procedure

Only XIENCE stent can be used for target lesion(s). Stent implantation procedure should be performed according to the instruction for use (IFU) of the XIENCE family stent used. If XIENCE stent is delivered beyond the guide catheter but not implanted, the subject should not be registered in the study. If other DES was implanted, the subject should not be registered in the study.

In this study, a maximum of three target lesions may be treated with a maximum of two target lesions per epicardial vessel. Non-target lesion (i.e., lesions that do not meet the angiographic eligibility criteria) treatments are not allowed during the index procedure.

Planned staged procedures are allowed (recommend to be performed within 30 days). The site may consent the subject after the initial procedure. Subject registration will occur once the last staged procedure is performed and the last staged procedure is considered as the index procedure. Post-procedure DAPT duration will be measured from the last staged procedure. Any planned stenting procedure must be done prior to subject registration. The subject must not have any additional stenting procedure planned after the index procedure.

Subjects may receive appropriate anticoagulation and other therapy according to standard hospital practice.

Overlapping stents are not allowed in the study, whether planned or for bailout. Subjects who received overlapping stents should not be registered in this study.

Lesion characteristics (lesion location, % diameter stenosis, TIMI flow, RVD, lesion length, thrombus presence, bifurcation or not, lesion complexity), device (device name, size, number of device implanted, bailout usage, overlapping stent) and procedural information (procedure time, access site, procedural anticoagulant and anti-thrombotic medications, any procedure complications) will be collected and recorded in eCRF.

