1.3.1 Selection of Control

The XIENCE V USA historical HBR control for 3-month DAPT study is derived based on the following criteria:

Definition of non-complex HBR from XIENCE V USA

- HBR inclusion criteria (any one of the below HBR criteria):
 - Age \geq 75 years
 - History of major bleeding
 - History of stroke
 - Receiving or scheduled to receive chronic anticoagulation therapy
 - Renal insufficiency (creatinine $> 2\text{mg/dl}$)
 - Anemia (Hb $< 11\text{g/dl}$ or transfusion)
 - Thrombocytopenia (platelet count $< 100,000/\text{mm}^3$)
- Exclusion criteria for non-complex:
 - STEMI
 - LVEF $< 30\%$
 - Patients with more than 3 lesions treated during index procedure
 - Patients with more than 2 vessels treated during index procedure

- At least one lesion with RVD < 2.25 mm or > 4.25 mm (visual estimation)
- At least one lesion located in left main
- At least one lesion located in graft
- At least one in-stent restenosis lesion
- At least one lesion containing thrombus
- At least one target lesion having TIMI flow 0
- At least one target lesion with length > 32 mm by visual estimation.

The above selection criteria for the XIENCE V USA historical control aligns with the key inclusion/exclusion criteria of the XIENCE 90 Study.

For primary analysis, the XIENCE V USA non-complex HBR control subjects must be also 3-month clear, following the same logic as defined for the primary analysis population (refer to Section 1.4).

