1.4 Analysis Populations

Primary Analysis Population

The primary analysis population includes “3-month clear” population, defined as subjects who are free from myocardial infarction (modified ARC), repeat coronary revascularization, stroke, or stent thrombosis (ARC definite/probable) within 3 months [REDACTED]

[REDACTED] after stenting AND have been compliant with 3-month dual antiplatelet therapy

(DAPT) [REDACTED]

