2.1.3 Propensity Score

Given that subjects in the two comparison groups (XIENCE 90 vs XIENCE V USA) are not randomized and thus may not have balanced baseline characteristics, the non-inferiority and superiority tests for 3-12 month period will be carried out through stratified analysis in the “3-month clear” population. The stratification will be performed through propensity scores (PS). For each individual a propensity score (i.e., predicted probability between 0 and 1) for group (XIENCE 90) membership will be calculated using logistics regression, with “group” as the outcome and baseline variables including demographic, lesion characteristics, and risk factors as the predictors. Subjects will be categorized into 5 groups based on the calculated propensity scores and their quintiles. Non-inferiority and superiority will then be carried out for the rate of the endpoint using the method described in sections below stratified by the propensity quintiles.

The propensity score modeling and design will be performed by an independent statistician who has no access to any outcome data of both the XIENCE 90 study and the XV USA historical control for the integrity and interpretability of study results. The independent statistician will be blinded and have no access to clinical outcome and any follow-up information to avoid introducing bias into the analysis.

[REDACTED]

[REDACTED]

[REDACTED]

[REDACTED]

[REDACTED]

Per the recent publication by Yue et al²⁸ on two-stage study designs involving propensity score adjustment, the propensity score calculation results will subsequently be sent to the FDA for review and approval prior to performing the primary endpoint and major secondary endpoint analyses.

[REDACTED]

2.1.3-1 Propensity Score Variable List

Based on prior clinical experience and clinical research, below is the list of variables that are considered to be related to assignments modeling building:

- Gender
- Age
- Creatinine
- Chronic anticoagulant
- History of stroke
- History of major bleeding
- Platelet
- Hb
- BMI
- Hypertension
- Dyslipidemia
- Prior PCI
- Prior CABG

- Prior MI
- Multivessel disease
- Clinical Presentation (ACS (NSTEMI, ACS unstable angina) vs. non-ACS)
- Diabetes
- ACC/AHA lesion complexity
- Total lesion length per patient
- RVD
- Diameter stenosis%
- Bifurcation
- Number of lesions treated
- Number of vessel treated
- Number of stents per patient
- Total stent length per patient
- Discharge P2Y12
- Paris bleeding score

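### The control selection in SAP 1.3.1 omits the procedural-success and overlapping-stent criteria that XIENCE 90 subjects must meet, which could tilt the comparison toward non-inferiority

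*Protocol*

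**What the plan says.** **XIENCE 90 arm.** Protocol 5.3.2.1, item 5, requires each target lesion to have been treated successfully: final in-stent residual stenosis under 20%, final TIMI-3 flow, no residual dissection of NHLBI type B or worse, "no transient or sustained angiographic complications (e.g., distal embolization, side branch closure"), no chest pain beyond 5 minutes, and no ST-segment elevation above 0.5 mm or depression persisting beyond 5 minutes. Protocol 5.3.2.2, item 6, excludes overlapping stents, and the note below it extends the angiographic criteria to every target lesion. On timing, Protocol 5.4 states: "Subject registration will occur after the index procedure but prior to discharge and up to 3 days post index procedure".

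**Control arm.** SAP 1.3.1 selects XIENCE V USA subjects on high-bleeding-risk status, STEMI, LVEF, numbers of lesions and vessels treated, reference diameter, left main, graft, in-stent restenosis, thrombus, TIMI 0 flow and lesion length. It then says: "The above selection criteria for the XIENCE V USA historical control aligns with the key inclusion/exclusion criteria of the XIENCE 90 Study". For the primary analysis, "the XIENCE V USA non-complex HBR control subjects must be also 3-month clear". Under SAP 1.4 that means "free from myocardial infarction (modified ARC), repeat coronary revascularization, stroke, or stent thrombosis (ARC definite/probable) within 3 months", plus compliance with DAPT.

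**Adjustment.** SAP 2.1.3 introduces its covariates with the words "below is the list of variables that are considered to be related to assignments modeling building". The list has no entry for final TIMI flow, dissection, procedural complication, chest pain or ST change. The nearest entry is "Diameter stenosis" (as a percentage), with no stated time point.

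**The concern.** Entry to one arm depends on an outcome of the procedure, and entry to the other does not. By protocol no XIENCE 90 subject fails item 5, so controls who would fail it have no counterpart in any propensity quintile. Adding a covariate would not create the missing overlap; only restricting the controls does.

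If those controls carry a higher risk of death or MI between 3 and 12 months, the control rate is raised for a reason unrelated to DAPT duration. The 3-month DAPT arm would then look better by comparison, and non-inferiority would be easier to declare. The alignment sentence in SAP 1.3.1 would lead a reader to think this had been dealt with.

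**Working it through.** **1. Criteria side by side**

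| Element | XIENCE 90 (Protocol 5.3.2.1 item 5; 5.3.2.2 item 6) | Control list (SAP 1.3.1) | Propensity list (SAP 2.1.3) |
|---|---|---|---|
| Final residual stenosis | under 20% | none | a diameter-stenosis entry, time point not stated |
| Final TIMI flow | 3 | none | none |
| Residual dissection | none of type B or worse | none | none |
| Angiographic complication | none, even transient | none | none |
| Chest pain, ST change | limits set | none | none |
| Overlapping stents | excluded | none | number of stents and total stent length, at most proxies |

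The TIMI 0 item in the control list mirrors the lesion exclusion in Protocol 5.3.2.2, item 4; it is not a test of final flow. Protocol 6.2 collects procedural complications in XIENCE 90, but SAP 2.1.3 does not list them. The readable parts of SAP 2.2.1 and 2.9 contain no sensitivity analysis on procedural result.

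**2. What the plan's own figures allow.** SAP 1.5 gives 2,000 XIENCE 90 subjects and about 1,150 3-month-clear controls. The margin, expected rates, power and attrition are blacked out in the public copy, so the sample size cannot be reproduced. That is not a fault in the plan.

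**3. Bias formula.** Let p be the 3-12 month death/MI rate in controls with a successful result, f the share of 3-month-clear controls who would fail the criteria, and RR their relative risk in that window.

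- Control rate = p(1 − f) + p·f·RR
- Bias = p·f·(RR − 1)

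All three inputs are assumptions: p = 7%, f = 3-10%, RR = 1.5-2.0, with RR = 1 as the null case.

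**4. Effect on the test.** The level is 0.025 (Protocol 9.4), taken as one-sided. I assume 1,800 of the 2,000 are 3-month clear, 1,150 controls and no stratification. SE is the unpooled standard error of the difference, with the XIENCE 90 variance taken at p. Type I error at the margin = Φ(−1.96 + bias/SE).

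| f | RR | Bias (points) | SE (points) | Bias/SE | Type I error | Extra control events (bias × 1,150) |
|---|---|---|---|---|---|---|
| any | 1.0 | 0 | 0.96 | 0 | 0.025 | 0 |
| 3% | 1.5 | 0.07 × 0.03 × 0.5 = 0.105 | 0.97 | 0.11 | 0.032 | 1.2 |
| 10% | 1.5 | 0.07 × 0.10 × 0.5 = 0.35 | 0.98 | 0.36 | 0.055 | 4.0 |
| 3% | 2.0 | 0.07 × 0.03 × 1.0 = 0.21 | 0.97 | 0.22 | 0.041 | 2.4 |
| 10% | 2.0 | 0.07 × 0.10 × 1.0 = 0.70 | 0.99 | 0.71 | 0.105 | 8.1 |

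**5. Cost of filtering.** Controls fall from 1,150 to 1,150 × 0.97 ≈ 1,116 or 1,150 × 0.90 = 1,035. The SE ratio is √[(1/1,800 + 1/n) / (1/1,800 + 1/1,150)], which is 1.009 and 1.033. A nominal 80% power becomes Φ(2.80/1.009 − 1.96) ≈ 79% and Φ(2.80/1.033 − 1.96) ≈ 77%.

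**The case against.** The strongest reply is that the plan already deals with most consequences of a poor result. Controls must be 3-month clear, and the MI definition in Protocol Appendix II includes periprocedural MI. Embolization, side branch closure or prolonged ischaemia that led to an MI, stent thrombosis or repeat revascularization therefore removes the control, and the endpoint only starts at 3 months. The control is also not a raw all-comer group: SAP 1.3.1 removes STEMI, left main, graft, restenotic, thrombotic and long lesions, where complicated stenting might be expected. Lesion complexity, bifurcation, stent number and stent length are in the propensity list and may adjust in part. All of this stands, and it limits the bias. It does not close the gap, because the 3-month-clear rule acts on events and compliance, not on the stent result.

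A reader might go further in three ways that the documents do not support:

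- **That the comparison is biased toward non-inferiority as a matter of fact.** No passage shows that event-free controls with a suboptimal result have excess risk after 3 months. Without that excess, the bias is zero.
- **That nothing in the plan covers procedural result.** The time point of the diameter-stenosis entry is not given, and parts of SAP 2.1.3, 2.2.1 and 2.9 are blacked out and might bear on this.
- **That failed deliveries are a further source of bias.** Protocol 6.2 says: "If XIENCE stent is delivered beyond the guide catheter but not implanted, the subject should not be registered in the study". But the 3-month-clear period is counted from stenting, and the documents do not say whether XIENCE V USA retained such subjects or that they carry later risk.

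**Conclusion.** The mismatch in eligibility is documented, and the alignment sentence in SAP 1.3.1 is not accurate for Protocol 5.3.2.1 item 5 or 5.3.2.2 item 6. The bias is conditional. It needs excess death/MI risk after 3 months among controls who had a suboptimal result and no early event; its direction would then favour non-inferiority.

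Its size cannot be derived from the documents. Under the assumptions above it runs from about 0.1 to 0.7 points, equivalent to roughly 1 to 8 extra events among 1,150 controls. The nominal 0.025 error rate would become about 0.03 to 0.11. The upper end needs both the largest share and the largest relative risk together. This is worth correcting because the remedy is cheap, not because a material bias has been shown.

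**What to change.** In SAP 1.3.1, before the propensity model is built, have the outcome-blinded independent statistician named in SAP 2.1.3 exclude controls who fail Protocol 5.3.2.1 item 5 or 5.3.2.2 item 6, using the fields that XIENCE V USA recorded. Keep the unfiltered control set as a sensitivity analysis. Qualify the alignment sentence for any element not recorded, and state the time point of the diameter-stenosis variable in SAP 2.1.3.

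The cost is SAP wording and one filter on existing records, an assumed 3-10% fewer controls, an SE about 1-3% larger, and nominal 80% power falling to about 79-77%. Alignment will be only partial if XIENCE V USA lacks some fields; the documents do not say which it holds.

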### **5.3.2.2 Angiographic Exclusion Criteria**

1. Target lesion is in a left main location.
2. Target lesion is located within an arterial or saphenous vein graft.
3. Target lesion is restenotic from a previous stent implantation.
4. Target lesion is a total occluded lesion (TIMI flow 0).
5. Target lesion contains thrombus as indicated in the angiographic images (per SYNTAX score thrombus definition).
6. Target lesion is implanted with overlapping stents, whether planned or for bailout.

Note: If there is more than one target lesion, all target lesions must satisfy the angiographic eligibility criteria. Non-target lesion (i.e., lesions that do not meet the angiographic criteria listed above) treatments are not allowed during the index procedure.

### **5.4 Subject Registration**

Subject registration will occur after the index procedure but prior to discharge and up to 3 days post index procedure, upon confirmation of the following:

- Signed informed consent has been obtained;
- Subject has met all the inclusion and none of the exclusion criteria (including both general and angiographic criteria).

Planned staged procedures are allowed (recommend to be performed within 30 days). The site may consent the subject after the initial procedure. Subject registration will occur once the last staged procedure is performed, and the last staged procedure is considered as the index procedure.

### **5.5 Subject Discontinuation**

All registered subjects will be considered to have completed the study upon study completion of the 12-month follow-up.

Each registered subject shall remain in the trial until completion of the required follow-up period; however, a subject's participation in any clinical trial is voluntary and the subject has the right to withdraw at any time without penalty or loss of benefit. Conceivable reasons for discontinuation may include, but not be limited to, the following:

- Subject death
- Subject voluntary withdrawal
- Subject withdrawal by physician as clinically-indicated
- Subject lost-to follow-up as described below
- Subject's follow-up is terminated according to **Section 3.4** Early termination of the Clinical Trial

The Sponsor must be notified of the reason(s) for subject discontinuation. The site will record this information on the eCRF and source documents and provide this information to the Sponsor. Investigators must also report this to their respective IRB/EC as defined by their institution's procedure(s).

No additional follow-up will be required or data recorded from subjects once withdrawn from the trial, except for the status (deceased/alive).

However, if a subject withdraws from the study due to problems related to the investigational device safety or performance, the investigator shall ask for the subject's permission to follow his/her status/condition outside of the clinical investigation.

